2.2.1.3 Nonclinical toxicology

Product Name: PRN473 (SAR444727)

Dermal administration of PRN473 Gel to mini pigs at 0.5% (0.05 mg/cm²), 2% (0.2 mg/cm²), and 10% (1 mg/cm²), strengths for at least 28 days was well tolerated. There were no PRN473-related changes. The maximum tolerated dose was not reached even at the highest dose of 10% when administered QD over a 10 % body surface area (approximately 400 cm² at a gel application rate of 10 mg/cm²/day) of mini pig. At the low dose (0.5% gel) due to the low exposure levels, the kinetic properties of PRN473 were not able to be determined, except one animal on Day 28. The maximum concentrations observed on Day 7 and Day 28, following 10% gel application were 2.32 ng/mL and 3.17ng/mL, respectively. The corresponding area under the concentration-time curve (AUC) values were 11.3 ng×hr/mL and 25.1 ng×hr/mL, respectively. Additionally, the 10% PRN473 Gel did not cause ocular irritation and the PRN473 Gel may have the potential to be a contact sensitizer as discussed in the Investigators Brochure.

In a 28-Day oral rat study, all treated animals had measurable systemic exposure following both single and repeated QD oral PRN473 administration at doses of 150 and 500 ng/mL. PRN473 mean maximum plasma concentration (C_{max}) values increased less than proportionally and area under the plasma concentration-time curve from time zero to the last measurable concentration (AUC_{0-last} exposures increased proportionally with increases in dose. No significant accumulation was observed (as assessed by mean C_{max} and AUC_{0-last} on Day 28 vs Day 1). A higher exposure was observed in females then males as assessed by mean C_{max} and AUC_{0-last}. Treatment with PRN473 was well tolerated. Liver weight changes with associated hepatocellular hypertrophy were observed following oral treatment with 500 mg/kg. Based on these findings, the no-observed-adverse-effect level (NOAEL) in rats is considered 150 mg/kg (C_{max} : female 713 ng/mL, male 308 ng/mL; AUC: female 6600 ng×hr/mL, male 3170 ng×hr/mL).

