8.2.6 Local Cutaneous Tolerability

Grading of application site local tolerability symptoms will be recorded using the grading scale (Appendix 4, Section 10.4.1) following each dosing during the blinded period. Each target lesion will be graded within approximately 30 minutes after dosing by site staff or trained medical professional and a record of the worst symptom grade during time period will be recorded. During the Open Label period symptom grading will record worst symptom observed on the lesional areas treated within approximately 30 min after dosing.

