8.3.1.1 Definition of AE

AE Definition

- An AE is any untoward medical occurrence in a patient or clinical study participant, temporally associated with the use of study intervention, whether or not considered related to the study intervention.
- NOTE: An AE can therefore be any unfavorable and unintended sign (including an abnormal laboratory finding), symptom, or disease (new or exacerbated) temporally associated with the use of study intervention.

Events Meeting the AE definition

- Any abnormal laboratory test results (hematology, clinical chemistry, or urinalysis)
 or other safety assessments (eg, ECG, radiological scans, vital signs measurements),
 including those that worsen from baseline, considered clinically significant in the medical
 and scientific judgment of the Investigator (ie, not related to progression of underlying
 disease):
 - Symptomatic and/or
 - Requiring either corrective treatment or consultation, and/or
 - Leading to study intervention discontinuation or modification of dosing, and/or
 - Fulfilling a seriousness criterion, and/or
- Exacerbation of a chronic or intermittent pre-existing condition including either an increase in frequency and/or intensity of the condition.
- New conditions detected or diagnosed after study intervention administration even though it may have been present before the start of the study.
- Signs, symptoms, or the clinical sequelae of a suspected drug-drug interaction.
- Signs, symptoms, or the clinical sequelae of a suspected overdose of either study intervention or a concomitant medication.

• "Lack of efficacy" or "failure of expected pharmacological action" per se will not be reported as an AE or SAE. Such instances will be captured in the efficacy assessments. However, the signs, symptoms, and/or clinical sequelae resulting from lack of efficacy will be reported as AE or SAE if they fulfill the definition of an AE or SAE.

Events NOT Meeting the AE definition

- Any clinically significant abnormal laboratory findings or other abnormal safety assessments which are associated with the underlying disease, unless judged by the Investigator to be more severe than expected for the patient's condition.
- The disease/disorder being studied or expected progression, signs, or symptoms of the disease/disorder being studied, unless more severe than expected for the patient's condition.
- Medical or surgical procedure (eg, endoscopy, appendectomy): the condition that leads to the procedure is the AE.

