9.4.4.3 Local cutaneous tolerability

Signs of local cutaneous intolerability as incidence and severity of application-site burning/stinging, itching, and erythema will be summarized for the Blinded Period by treatment (PRN473 Gel, 5% or placebo) and overall for the open-label phase.

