3.6.3.2 Local cutaneous tolerability

The local cutaneous tolerability is assessed by the incidence and severity (grade) of application-site events such as burning/stinging, itching, and erythema.

Grading of application site local tolerability symptoms will be recorded using the grading scale (cf Protocol Appendix 4, Section 10.4.1) following each dosing during the blinded period. During the Open Label period symptom grading will record worst symptom observed on the lesional areas treated within approximately 30 min after dosing.

For each lesion, number and proportion of participants with at least one application-site event (such as burning/stinging, itching, and erythema) over the 2-week double-blind period, the 4-week Open label period, overall and by type of sign will be summarized. For each lesion, and by type of sign, the distribution of corresponding worst grade (intensity) will be summarized. The localization of the lesion on the body with an application-site event of local untolerability will be reported.

Burning/stinging sub-score assessments over time by lesion during blinded period and overall during Open-label period will be also summarized.

Overview of AEs linked to local cutaneous tolerability will be presented by SOC, PT for each study period and overall.

No analysis of the total score will be performed.

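### On the local tolerability scale only burning/stinging has a planned time course, so a later erythema or itch reaction at or below the lesion's earlier grade can be masked

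*SAP*

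**What the plan says.** - **Data collected.** Protocol 8.2.6 has each target lesion graded "following each dosing during the blinded period", within about 30 minutes after dosing. The scale in Protocol 10.4.1 covers burning/stinging, pruritus and erythema, each from 0 to 3. The Schedule of Activities gives no predose tolerability grade.
- **Protocol analysis.** Section 9.4.4.3 treats the three signs alike: incidence and severity of application-site "burning/stinging, itching, and erythema will be summarized for the Blinded Period by treatment". It specifies no time axis for any of them.
- **SAP analysis.** Section 3.6.3.2 gives, for each lesion, the "number and proportion of participants with at least one application-site event (such as burning/stinging, itching, and erythema) over the 2-week double-blind period", and likewise for the open-label period. It then adds: "For each lesion, and by type of sign, the distribution of corresponding worst grade (intensity) will be summarized". The only over-time summary on this scale is: "Burning/stinging sub-score assessments over time by lesion during blinded period and overall during Open-label period will be also summarized". No reason is given for choosing that one sign.
- **Hazard.** Protocol 2.2.1.3 states that "the PRN473 Gel may have the potential to be a contact sensitizer as discussed in the Investigators Brochure".
- **Status.** Local cutaneous tolerability is part of the primary endpoint (Protocol Table 3, SAP Table 1).

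**The concern.** Any event and worst grade carry no timing and are not referred to a starting value. That suits a sign that is absent before treatment. Erythema and itch are signs of the disease being treated: entry requires vIGA-AD 2 or 3 (Protocol 5.1), score 2 already describes slight but definite erythema among its features (Protocol 10.4.2), and grade 0 erythema on the tolerability scale means skin of normal colour (Protocol 10.4.1). Most lesions will therefore probably score at least 1 at the first grading.

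Take a lesion that starts at grade 2, settles, and reddens again to grade 2 late in the blinded period. In both tables it looks the same as a lesion that starts at grade 2 and improves steadily. If that happens on active lesions and not on their paired placebo lesions, a local signal on a primary endpoint has been recorded but does not appear in the tolerability tables. With at most 40 participants, a few such cases would be all the evidence available.

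**Working it through.** The plan gives no sample-size, power or reaction-rate figure on this point, so there is nothing to reproduce. The check is logic plus arithmetic.

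**Inputs from the documents.** Twice daily for 14 days gives 2 x 14 = 28 gradings per lesion. Up to 40 participants each have one active and one placebo lesion.

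**Assumptions, because the documents give none.**
- An event means grade 1 or above.
- Day 1 erythema grades 0/1/2/3 are split 10/50/35/5% (milder), 5/35/50/10% (middle) or 0/20/60/20% (more severe), with the same mix on both lesions.
- Both lesions otherwise improve by one grade by the late part of the blinded period, so the earlier maximum is the Day 1 grade.
- 4 of 40 active lesions (10%) then react, reaching grade r. Grading noise is ignored.

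**Step 1: when do the planned tables change?** Any event changes only if the Day 1 grade is 0. Worst grade changes only if the Day 1 grade is below r. The share of reactions leaving each table unchanged is therefore 1 - P(0) for any event and P(Day 1 grade >= r) for worst grade.

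| Unchanged by a late reaction | Milder | Middle | More severe |
|---|---|---|---|
| Any event, any r | 90% | 95% | 100% |
| Worst grade, r = 1 | 90% | 95% | 100% |
| Worst grade, r = 2 | 35+5 = 40% | 50+10 = 60% | 60+20 = 80% |
| Worst grade, r = 3 | 5% | 10% | 20% |

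**Step 2: what would the reader see?** If a share p of placebo lesions reaches grade r or more, the active share is p + 0.10 x (1 - p). For the worst-grade table p is P(Day 1 grade >= r). For a late-window table it is P(Day 1 grade >= r + 1), because of the one-grade improvement.

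| Placebo vs active | Milder | Middle | More severe |
|---|---|---|---|
| r = 2, worst grade >= 2 (planned) | 40 vs 46% | 60 vs 64% | 80 vs 82% |
| r = 2, late-window grade >= 2 | 5 vs 14.5% | 10 vs 19% | 20 vs 28% |
| r = 3, worst grade 3 (planned) | 5 vs 14.5% | 10 vs 19% | 20 vs 28% |
| r = 3, late-window grade 3 | 0 vs 10% | 0 vs 10% | 0 vs 10% |

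For grade 2, the planned table shows an excess of 6, 4 or 2 points. That is 2.4, 1.6 or 0.8 of the 4 reacting participants (points/100 x 40). The late window shows 9.5, 9 or 8 points, or 3.8, 3.6 or 3.2 participants. For grade 3, the planned table already shows 3.8, 3.6 or 3.2 of the 4.

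For grade 1, the late window gives 40 vs 46%, 60 vs 64% and 80 vs 82%, so it too would miss many; the planned worst-grade table shows at most 1 point (90 vs 91% in the milder mix).

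**Step 3: would there be cases to see?** The chance of at least one among 40 is 1 - (1 - q)^40: 64% for q = 2.5%, 87% for 5% and 99% for 10% (assumed rates). With none observed, the one-sided 95% upper limit is 1 - 0.05^(1/40) = 7.2%. Single cases therefore carry weight.

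**The case against.** The best defence is that the SAP does more than the protocol asks and covers erythema and itch elsewhere. Protocol 9.4.4.3 requires only incidence and severity by treatment. Burning/stinging is the sign not otherwise measured as disease, so it is a natural choice for a time course. Itch is followed daily by lesion to Day 15 through lesional PP-NRS, and erythema is one of four TSS items compared at Days 8 and 15 (SAP 3.4). AEs are listed with onset date (Protocol 9.4.4.2), and exacerbation of a pre-existing condition can be an AE (Protocol 8.3.1.1). SAP 3.6.3.2 adds an overview of AEs linked to local tolerability, and an allergic reaction to the product is a listed stopping rule (Protocol 7.1.1).

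Much of this stands, and it rules out three stronger readings that a reader might infer.
- **That the SAP follows only burning/stinging over time.** This is true of the tolerability scale but not of the SAP as a whole.
- **That a late reaction is hidden outright.** A reaction above the earlier maximum raises the worst grade on the active lesion, and most grade 3 reactions would show in the arithmetic above.
- **That sensitisation is an established hazard with a known late onset.** The protocol says only that the gel may have the potential and refers to the Investigator's Brochure. Neither document gives a timing. The point needs only a reaction that follows an equal or higher grade.

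The other routes remain partial substitutes. PP-NRS and TSS are efficacy summaries by treatment in participants with at least 80% dosing (SAP Table 2). Data after discontinuation are not considered, and no separate analysis of the TSS erythema item is planned. The AE definition excludes "The disease/disorder being studied or expected progression, signs, or symptoms of the disease/disorder being studied" unless more severe than expected, and an eczema-like reaction on an eczema lesion could be read that way. Assigning blinded-period TEAEs to a lesion's treatment is optional (SAP 3.6.2). Photographs are not used to evaluate AEs (Protocol 8.9). After Day 14 no placebo lesion remains, and the schedule marks tolerability grading only at Days 15 and 29.

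**Conclusion.** The point holds in a limited form. On the tolerability scale, erythema and pruritus are summarised in a way that can mask a reaction on the active lesion at or below that lesion's earlier grade. The gap is firmest for erythema at grade 2 or below, because itch has daily lesional PP-NRS as partial cover and higher-grade reactions mostly show. Under the assumed mixes, worst grade is unchanged by 40-80% of late grade 2 reactions and 5-20% of grade 3 reactions, and any event by 90-100% of either.

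These figures are illustrative. They rest on an assumed Day 1 grade mix, equal improvement on both lesions and no grading noise. If the active lesion improves faster and grades fluctuate, the placebo lesion has more chances of reaching a high grade, which would offset part of an excess on active.

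This is a worthwhile, inexpensive improvement to the reporting of a primary safety endpoint. It is not a contradiction between the documents and not a flaw in data collection.

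**What to change.** In SAP 3.6.3.2:

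1. Replace the burning/stinging-only time course for the blinded period with a summary over time of burning/stinging, pruritus and erythema grades by lesion treatment: active, placebo and the within-participant difference.
2. Add a listing of participants whose erythema or pruritus grade on either target lesion rises after an earlier on-treatment fall, with the grades of the paired lesion alongside. The SAP should state in advance how large or how sustained a rise must be; the documents give no basis for a particular threshold.

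The cost is one extended table and one listing, with no new data, visits or staff. With 28 gradings per lesion, natural flares and one-grade fluctuations will also be listed; the placebo lesions show how often that happens. Milder reactions, especially at grade 1, will still be hard to separate from disease. No change is proposed to the AESI list or to any clinical rule.

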3.7 OTHER ANALYSES

3.7.1 Other variables and/or parameters

3.7.1.1 *PK analyses*

For PK concentrations, the arithmetic mean, SD, median, minimum, maximum, percent coefficient of variation (CV%), geometric mean, geometric coefficient of variation (geometric CV%), and the number of observations below LLOQ values will be presented by timepoint. For the purpose of calculating summary statistics, plasma concentrations (and applicable metabolites) that are below the LLOQ will be set to 0 for both pre-dose and post-dose samples excepted for the geometric mean and associated coefficient of variation for which they will be considered as missing. Additional analyses will be performed as deemed necessary upon review of the data.

Graphical displays of concentrations over time may also be presented.

3.7.1.2 *Biomarkers analyses*

Statistical analyses of biomarkers (RNAseq data, proteomic data...) will be exploratory in nature and will be detailed in a Biomarker SAP and results may be analysed separately.

3.8 INTERIM ANALYSES

An interim analysis (IA) for internal decision making will be implemented when approximately 25 or more of the planned participants have completed the Blinded Period (Day 15). Available data of the Open Label Period may be included in the analysis as appropriate.

The outcome is meant for internal decision making and may lead to early termination of the study only in case of unfavorable signals, or continuation without any changes.

3.8.1 General considerations for the interim analysis

The Sponsor team that will analyze the data will include: a Medical Monitor, a biostatistician, a programmer, and a safety designee (global safety officer, [GSO]). Only the biostatistician and the programmer will have the access to unblinded individual data at the time of the analysis, which will not be provided to other Sponsor team members reviewing the data. Results will be provided in a restricted way following a dissemination plan, issued before any treatment code release for the analysis established upfront before the unblinding. The blinding will be preserved notably toward the Investigator, other site staff involved in the conduct of the trial, and participants.

The results of this IA will be considered preliminary results as they will not be based on final data. Final analysis will be conducted after database lock for the clinical study report.

Analyses methods and conventions described in the other sections of this SAP will be applied for all analyses as applicable.

3.9 CHANGES TO PROTOCOL-PLANNED ANALYSES

No major statistical changes were included in the protocol amendment(s).

One major statistical change in SAP to the current amended protocol has been made and is summarized in the section below:

Major statistical changes in SAP to (current) amended protocol

Current Amended Protocol Number	Section	Changes	Rationale
	2- Analysis Populations	Delete ITT population Redefine Efficacy population	ITT population is not used in the analysis Efficacy population has been redefined to take into account compliance during both periods (double-blind and open-label period)

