9.3 ANALYSIS SETS

For the purposes of analysis, the following analysis sets are defined:

Table 7 - Analysis sets

Patient Analysis Set	Description
Screened	All patients who signed the ICF.
Enrolled/Randomized	All patients from the screened population who have been allocated to a randomized intervention by IRT regardless of whether the intervention was received.
Safety	All randomized patients who receive any amount of study intervention (PRN473 or placebo) will be included in the Safety population. The Safety population will be based on the intervention actually received and will be used for the summaries of all safety assessments.
Pharmacokinetic	All patients who received any amount of active study intervention (PRN473) and have at least one PK sample taken will be included in the PK population. The PK population will be used for the summaries of all PK data.
ITT	All randomized patients who did actually receive at least 1 complete dose of study intervention with at least 1 post-study intervention administration measurement, with available efficacy.
Efficacy	All randomized patients who did actually receive at least 80% of prescribed study intervention in the Blinded Period and/or at least 80% of prescribed study intervention in the Open-Label Period and with at least 1 post-study intervention administration efficacy measurement in the corresponding period, Patients will be analyzed according to the intervention they actually received.
Biomarker	All patients with no important deviations impacting Biomarker measurements, for whom the Biomarker data are considered sufficient and interpretable.

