9.4.3 Analysis of efficacy data

Efficacy analyses will be based on the Efficacy population. A patient will be considered evaluable per endpoint and study period, if they receive at least 80% of prescribed study intervention in that period and have a post-baseline assessment of the corresponding endpoint for that period (ie, after Day 1 or after Day 15).

Where appropriate, supplemental analyses will be presented excluding observations after administration of rescue medication. Imputation would then be performed for missing observations including those due to withdrawal due to lack of efficacy, as will be specified in the SAP.

Efficacy analyses will be an early explorative assessment and performed without the aim of formal inferential statistics. No adjustment will be made for multiple analyses.

Treatment differences or ratios will be assessed for PRN473 Gel, 5% versus placebo, mainly at Day 15. Data will be presented by treatment for the Blinded Period where assessed per lesion, and overall otherwise, as well as for the Open-Label Period.

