
2 ANALYSIS POPULATIONS

The following populations for analyses are defined:

Table 2 - Populations for analyses

Participants Analysis Set	Description
Screened	All participants who signed the informed consent form (ICF).
Enrolled/Randomized	All participants from the screened population who have been allocated to a randomized intervention for each target lesion by interactive response technology (IRT) regardless of whether the intervention was received.
Safety	All randomized participants who receive any amount of study drug (SAR444727 or placebo) will be included in the Safety population. The Safety population will be based on the intervention actually received and will be used for the summaries of all safety assessments.
Pharmacokinetic	All participants who received any amount of active study drug (SAR444727) and have at least one pharmacokinetics (PK) sample taken will be included in the PK population. The PK population will be used for the summaries of all PK data.
Efficacy	
- For double blind periodAll randomized participants who did actually receive at least 80% of prescribed study drug in the Blinded Period (for both lesion) and with at least 1 post-study drug administration efficacy (TSS) measurement.- For open label periodAll randomized participants who did actually receive at least 80% of prescribed study drug in the Blinded Period (for both lesion) and at least 80% of prescribed study drug in the Open-Label Period and at least 1 post-study drug administration efficacy (TSS) measurement.Participants will be analyzed according to the intervention they actually received.
Biomarker	All randomized participants with no important deviations impacting Biomarker measurements, for whom the Biomarker data are considered sufficient and interpretable.

Note: “Screened” means a participant's, or their legally acceptable representative's, agreement to participate in a clinical study following completion of the informed consent process.

Participants exposed to study intervention before or without being randomized will not be considered randomized and will not be included in any analysis population. The safety experience of these participants will be reported separately.

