3.4 TERTIARY/EXPLORATORY ENDPOINT(S) ANALYSIS

There are two type of exploratory endpoints. The first exploratory endpoint is biomarker to evaluate changes in blood samples, skin tape stripplings, and skin biopsies. Details are given in [Section 3.7.1.2](#).

The second exploratory endpoints are efficacy endpoints during double-blind period and Open-label period based on the efficacy population. For the double-blind period, treatment differences or ratios will be assessed for SAR444727 Gel, 5% versus placebo at Day 8 and Day 15, and data will be presented by treatment for the blinded period, for scores assessed per lesion, and overall otherwise. During the Open-Label Period, efficacy will be assessed mainly at Days 29 and 43,

overall. For TSS, data will be described over the full course of the study presented by treatment received during the double-blind Period.

More specifically, the following endpoints will be assessed:

During double-blind period

- Change from Baseline in lesional TSS for the 2 target lesions at Day 8 and Day 15
- Change from Baseline in daily lesional Peak Pruritus Numeric Rating Scale (PP-NRS) score for the 2 target lesions up to Day 15 and at Day 15
- Change from Baseline in lesional validated Investigator Global Assessment for AD (v-IGA-AD) score for the 2 target lesions at Days 8 and 15
- Lesional v-IGA-AD response (proportion of participants with a lesional v-IGA-AD score of 0 [clear] or 1 [almost clear] and ≥ 2 -grade improvement from Baseline) at Days 8 and 15

During Open-label period

- For lesional TSS
 - Change from Baseline in lesional TSS for the 2 target lesions at Days 29 and 43
 - Change from Day 15 in lesional TSS for the 2 target lesions at Days 29 and 43
- For PP-NRS
 - Change in daily global PP-NRS from Day 15 to Days 29 and 43
 - Change in weekly average of PP-NRS from Day 15 to Days 29 and 43
 - Proportion of participants achieving at least 3-point reduction from Day 15 in daily global PP-NRS at Days 29 and 43 in participants with PP-NRS ≥ 3 at Day 15
 - Proportion of participants achieving at least a 4-point reduction from Day 15 in daily global PP-NRS at Days 29 and 43 in participants with PP-NRS ≥ 4 at Day 15
- For Eczema Area and Skin Severity Index (EASI)
 - Percent change from Baseline in EASI at Days 29 and 43
 - Percent change from Day 15 in EASI at Days 29 and 43

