Participants with missing data at Baseline will not be included in the analysis. Participants with one or more post-dose timepoints will be included. Mixed model for repeated measures (MMRM) to account for missing data is used for the primary analysis under the missing at random (MAR) framework. Parameters will be estimated using restricted maximum likelihood method with the Newton-Raphson algorithm. Denominator degrees of freedom will be estimated using Kenward-Roger adjustment. All efficacy data after discontinuation of treatment will not be considered.

The same analysis will be conducted for lesional v-IGA-AD score at Days 8 and 15 and lesional PP-NRS. For the other efficacy parameters, only descriptive analyses will be provided.

The weekly average PP-NRS scores will be defined as the average of daily non-missing scores within the week preceding the given visit and will be calculated if there is a minimal amount of 4 non-missing scores.

The POEM score is a 5-point scale: 0 (“No days”), 1 (“1-2 days”), 2 (“3-4 days”), 3 (“5-6 days”) and 4 (“Every day”). The POEM score is calculated by summing the values for the 7 items.

If two or more questions are left unanswered the questionnaire is not scored.

The DLQI is a 4-point scale: 0 (“Not relevant”/“Not at all”), 1 (“A little”), 2 (“A lot”), 3 (“Very much”). For Question 7, “Prevented work or studying” is scored at 3. The DLQI is calculated by summing the score of each question.

The EASI-50/75/95/100 response is defined as a participant achieved a decrease by at least 50%/ 75%/ 95%/100% of EASI from Day 15.

Change in lesional TSS, PP-NRS (daily global and weekly average), EASI, BSA, SCORAD, POEM, DLQI during the Open label period will be analyzed descriptively. Estimations with 95% and 80% CIs may be derived. Sub-score of EASI by localization will also be provided.

Supplemental analyses

Where appropriate, supplemental analyses may be presented excluding observations after administration of rescue medication. No imputation will be made.

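### Every efficacy analysis is confined to participants with at least 80% of their doses; the SAP tightens the rule for open label and plans no run on a wider set

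*SAP*

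**What the plan says.** - **Set used.** SAP 3.4: "The second exploratory endpoints are efficacy endpoints during double-blind period and Open-label period based on the efficacy population".
- **Blinded period.** SAP 2, Table 2 admits randomised participants who "did actually receive at least 80% of prescribed study drug in the Blinded Period (for both lesion") and who have a post-dose TSS.
- **Open label.** The same table repeats the blinded-period condition and adds "and at least 80% of prescribed study drug in the Open-Label Period and at least 1 post-study drug administration efficacy (TSS) measurement".
- **Declared change.** SAP 3.9 lists deletion of the ITT set and redefinition of the Efficacy set as its one major change. The reason for the deletion is "ITT population is not used in the analysis"; the reason for the redefinition is to reflect compliance in both periods.
- **Model.** SAP 3.4 uses a mixed model under missing at random to deal with missing data and states: "Participants with one or more post-dose timepoints will be included". Efficacy values recorded after treatment stops are not used.
- **Compliance formula.** SAP 3.6.1 divides compliant administrations by those planned between the first and the actual last administration.
- **Protocol.** Section 9.4.3: "Efficacy analyses will be based on the Efficacy population", with evaluability judged per endpoint and per period at 80%. Table 7 in section 9.3 defines the Efficacy set by "at least 80% of prescribed study intervention in the Blinded Period and/or at least 80% of prescribed study intervention in the Open-Label Period". Its ITT set is "All randomized patients who did actually receive at least 1 complete dose of study intervention", with at least one post-dose measurement. No analysis in section 9.4 is assigned to that set.

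**The concern.** Whether a participant reaches 80% is known only after randomisation and can depend on how the lesions behave. Protocol 7.1.1 requires permanent discontinuation for an allergic reaction associated with the product and for certain adverse events, and protocol 9.4.3 anticipates withdrawal for lack of efficacy. Selecting on compliance can therefore select on outcome.

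The mixed model was chosen to use partial data, yet the set definition can remove participants with partial data before the model sees them. No analysis on a wider set would show whether this matters. At stake are the estimated TSS difference with its 95% CI, the open-label response proportions, and the interim analysis, to which SAP 3.8.1 applies the same conventions at about 25 completers of the Blinded Period.

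**Working it through.** The plan gives no figure to reproduce: the sample size is up to 40 without a calculation, and no dropout or compliance rate is stated.

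**1. Where the rule comes from**

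| | Protocol | SAP |
|---|---|---|
| Blinded-period efficacy | 80% in that period | 80% in that period, both lesions |
| Open-label efficacy | 80% in that period | 80% in both periods |
| Wider efficacy set | ITT defined, no analysis assigned | deleted |

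Example: a participant with 22 of 28 blinded applications (22/28 = 79%) and all 56 open-label applications is evaluable for open label under protocol 9.4.3, but leaves every open-label table under SAP Table 2.

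**2. Dose thresholds if the denominator is all prescribed applications**

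- Blinded: 2 × 14 = 28; 0.8 × 28 = 22.4, so 23, reached on the morning of Day 12. Before the Day 8 predose TSS, 2 × 7 = 14 have been given (50%).
- Open label: 2 × 28 = 56; 0.8 × 56 = 44.8, so 45.

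Stopping after the Day 8 assessment and before application 23 therefore discards an observed Day 8 score on both lesions.

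**3. The two denominators disagree**

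- Stops after 16 applications, none missed: 16/28 = 57% of prescribed, so excluded; 16/16 = 100% under SAP 3.6.1, so kept.
- Misses six at intervals but takes the last one: 22/28 = 79% on both readings, so excluded, with any observed Day 8 and Day 15 scores.

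Table 2 does not say which denominator applies. On either reading some observed post-dose data are dropped.

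**4. Blinded contrast**

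Simulation, 40 patients, 4,000 runs. None of these inputs comes from the documents: SD 2.0 TSS points; correlation 0.6 between visits and 0.5 between lesions; dropout after Day 8 with log-odds rising by 1 per TSS point of poorer Day 8 response on the driving lesion. The compliers-only paired difference at Day 15 was compared with a likelihood-type estimate using every Day 8 value. With no true effect and dropout driven by the active lesion:

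| Nominal dropout | Mean kept of 40 | Compliers-only bias (its SD) | All patients |
|---|---|---|---|
| 5% | 34.6 | −0.108 (0.333) | 0.002 |
| 10% | 31.9 | −0.163 (0.358) | −0.006 |
| 20% | 28.0 | −0.221 (0.373) | −0.002 |

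Negative values favour active. Actual exclusion exceeds the nominal rate: (40 − 34.6)/40 = 13.5% up to (40 − 28.0)/40 = 30%. The bias is 0.108/0.333 = 0.32 to 0.221/0.373 = 0.59 of the estimate's SD. When the placebo lesion drove dropout the sign reversed (0.103 to 0.225). When dropout was random or depended equally on both lesions the bias was within 0.01. Dropout depended only on observed Day 8 values, so missing at random held by construction. The all-patient estimate was no more precise in the table's scenarios (SD 0.338 to 0.393); its gain is in bias.

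**5. Open label**

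- Set size, assuming independent compliance of 80–95% (blinded) and 70–90% (open label): both-periods rule 40 × 0.80 × 0.70 = 22.4 to 40 × 0.95 × 0.90 = 34.2; per-period rule 40 × 0.70 = 28 to 40 × 0.90 = 36.
- CI width: √(40/32) = 1.12 and √(40/28) = 1.20, so 12% and 20% wider.
- Proportion, assuming 12 responders among 40 and that all 4 to 10 excluded are non-responders: 12/40 = 30% becomes 12/36 = 33% to 12/30 = 40%.

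**6. Would a wider set alone undo that shift?**

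Not for early stoppers. Someone who stops before the Day 29 window (Days 25–33, SAP Table 6) has no usable Day 29 value: later data are not used, an empty window is missing, and the SAP gives no imputation rule for responder endpoints. The wider set alone still yields 12/36 to 12/30; counting missing as non-response gives 12/40.

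**The case against.** The strongest reply is that little has been lost. Efficacy is exploratory, no hypothesis is tested, and the primary safety analysis covers everyone who received any study drug, so a reaction that stops treatment is still reported. Blinded doses are given under supervision, and both lesions of a participant leave together, which protects the within-patient contrast. SAP 3.9 declares the redefinition openly. The sentence admitting anyone with one post-dose timepoint can also be read as applying within the Efficacy set, where a participant with 23 or more doses may still miss a visit.

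Most of this stands. It limits the weight of the point and rules out calling the model sentence a flat contradiction. It does not supply a run that shows what the restriction does.

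Four stronger readings are tempting but unsupported:

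- **That the SAP replaced an ITT analysis with a compliers analysis.** The protocol already based efficacy on an 80% set and gave the ITT set no analysis.
- **That the ITT set would give a check against all randomised patients.** It needs a complete dose and a post-dose measurement, so it is in effect a modified ITT.
- **That early stoppers are certainly removed.** Under the SAP 3.6.1 formula they stay, and mainly intermittent non-compliers go.
- **That the blinded result is tilted towards active.** The direction depends on which lesion drives exclusion, and symmetric exclusion gives almost no bias.

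**Conclusion.** The point holds as a modest one. All planned efficacy results describe participants who met a post-randomisation compliance threshold. The SAP extends that threshold to both periods for open label, removes the only wider efficacy set, and plans no run to show the effect.

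How much Day 8 data is lost depends on a denominator that Table 2 and SAP 3.6.1 leave unreconciled. In the blinded period, bias needs exclusion that depends unequally on the two lesions. Under the assumed inputs it was about 0.10 to 0.23 TSS points on a 0–12 scale, in either direction. In open label there is no control, so the issue is selective description: proportions rise if those excluded respond less and fall if they respond more. The move from 30% to 33–40% is an assumed worst case, not a forecast.

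The point still merits action because the same conventions govern an interim analysis that may end the study, and because with at most 40 participants a few exclusions count.

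**What to change.** 1. Restore the protocol's ITT set, described as all dosed participants with at least one post-dose efficacy measurement. Run the blinded-period mixed models for TSS, lesional vIGA-AD and lesional PP-NRS on it, at minimum as a pre-specified sensitivity analysis. Keep the 80% set as supportive.
2. Present the open-label responder tables on that wider set as well. In that run, count participants without a usable value at the visit as non-responders.
3. Define the 80% denominator once, so that SAP Table 2 and SAP 3.6.1 agree.

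The cost is SAP wording, a simple missing-response rule and one extra run of existing programs. Open-label proportions may come out slightly less favourable. No extra data collection or change to trial conduct is needed.
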